5.1.3 Continued Eligibility Confirmation for subsequent vaccination

The following events constitute absolute contraindications to rotavirus vaccination and all participants should be evaluated for these before administration of second dose of the study vaccine. If any of these events occur during the study, the participant must not receive additional doses of the vaccine but should be appropriately followed up for safety by the Investigator.

- Hypersensitivity reaction following the administration of the study vaccine.
- Any uncorrected congenital malformation of the gastrointestinal tract (such as Meckel's diverticulum) which is diagnosed after the first vaccination and that would predispose for intussusception.
- Infants with any history of intussusception.
- Severe combined immunodeficiency (SCID).
- Detection of one or more of the exclusion criteria during dosing period.

The following events constitute contraindications to administration of the study vaccine at that point in time; if any of these events occur at the time scheduled for vaccination, the participant may be vaccinated at a later date or withdrawn at the discretion of the Investigator.

- Acute disease and / or fever at the time of vaccination.
 - Acute disease is defined as the presence of a moderate or severe illness with or without fever. All vaccines can be administered to persons with a minor illness such as mild upper respiratory infection without fever.
 - Fever is defined as temperature $\geq 37.5^{\circ}$ C (99.5°F) on axillary setting.
- Gastroenteritis within 72 hours preceding the study vaccine administration.

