17 PROTOCOL DEVIATIONS

Any changes from protocol-specified procedures and study-related SOPs occurring during the conduct of the trial will be documented and reported as protocol violations or deviations.

A Protocol Violation is any departure from the approved protocol, trial documents or any other information relating to the conduct of the study which may affect the safety of trial participants or the study outcomes. Examples include wrong randomization or enrollment of participants that do not meet inclusion / exclusion criteria.

A Protocol Deviation is any departure from the approved protocol, trial documents or any other information relating to the conduct of the trial that does not result in harm to the trial participants and does not significantly affect the study outcomes. Examples of deviations include a protocol

visit date outside the study visit window or an isolated incident of a missed or incomplete study procedure or study evaluation. Serious or repeated protocol violations or deviations will require assessment of the root cause and implementation of corrective and preventive action plans. They may constitute grounds to interrupt the trial at a study site.

The noncompliance may be either on the part of the participant, the investigator, or the study clinic staff. As a result of any deviations, corrective actions are to be developed by the site and implemented promptly. Trial procedures shall not be changed without the consent of POLYVAC/PATH. Deviations of the protocol will be examined on an individual basis, taking into account recorded information for the reason(s) that the deviation occurred.

It is the responsibility of the site to use continuous vigilance to identify and report deviations to CRO in a timely manner after identification. If required, reports of protocol deviations must be sent to the research ethics committees overseeing the research. The PI and his/her staff are responsible for knowing and adhering to their research ethics committee's/IRB's requirements.

To limit the potential for protocol deviations, the trial site will receive training (or retraining, as necessary) on protocol implementation and will operate according to written procedures.

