7.1 Analysis Populations

Definitions of analysis populations used are:

Enrolled Population: The enrolled population is defined as all screened participants who provide informed consent and are eligible for study participation, regardless of the participant's randomization and treatment status in the study.

Full Analysis (FA) population: The full analysis population is defined as all participants in the enrolled population who were randomized, received the first dose of the study vaccination, and provided at least one evaluable serum sample. The analysis based on this population will serve as supportive results for all immunogenicity objectives.

Participants in the FA population will be analyzed "as randomized", i.e. according to the vaccine a participant was designated to receive, which may be different from the vaccine that the participant actually received.

Per Protocol (PP) population: The per-protocol population is defined as all participants in the FA population who correctly received both study vaccines per randomization with no major protocol deviations that are determined to potentially interfere with the immunogenicity assessment of the study vaccines. This population will serve as the primary analysis population for all immunogenicity objectives. The criteria for exclusion of participants from the PP population is described in Section 10, Table A2, of this SAP.

Safety population: The safety population is defined as all participants in the enrolled population who received at least one dose of study vaccination and had any safety data available.

Participants in the safety population will be analyzed as “treated”, i.e. according to the actual vaccine received at the first dose. All safety analyses will be performed using this population. The denominators for different safety endpoints may vary according to the number of participants with available data for the specific endpoint. For instance, the solicited adverse event endpoints will be based only on those who have the corresponding CRF data regardless of other safety follow-up data.

The immunogenicity primary and secondary endpoints will be performed on the PP and FA population. Safety primary and secondary endpoints will be performed on the safety population. All other baseline and safety analyses, unless stated otherwise, will be performed on the safety population.

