10.	Did not meet I-E criteria but randomized	Participant met exclusion criterion	Participant met exclusion criterion 6: Any systemic disorder cardiovascular, pulmonary, hepatic, renal, gastrointestinal, hematological, endocrine, immunological, dermatological, neurological, cancer or autoimmune disease) as determined by medical history and/or physical examination which would compromise the child's health or is likely to result in non-conformance to the protocol.	PD review	Decision will be taken on the case by case basis during the review of final protocol deviation listing performed prior to database lock
11.	Did not meet I-E criteria but randomized	Participant met exclusion criterion	Participant met exclusion criterion 7: History of congenital abdominal disorders, intussusception, abdominal surgery	No PD review	Include
12.	Did not meet I-E criteria but randomized	Participant met exclusion criterion	Participant met exclusion criterion 8: Known or suspected impairment of immunological function based on medical history and physical examination.	No PD review	Exclude
13.	Did not meet I-E criteria	Participant met exclusion criterion	Participant met exclusion criterion	No PD review	Include

N	Protocol Deviation Category	Protocol Deviation Subcategory	Detailed Exclusion Description	PD Assessment	Decision for Per Protocol Population
	but randomized		9: Household contact with an immunosuppressed individual or pregnant woman.		
14.	Did not meet I-E criteria but randomized	Participant met exclusion criterion	Participant met exclusion criterion 10: Prior receipt of rotavirus or an intent to receive this vaccine from outside of the study center during study participation.	No PD review	Exclude
15.	Did not meet I-E criteria but randomized	Participant met exclusion criterion	Participant met exclusion criterion 11: Prior receipt of EPI vaccination during past 7 days or plan to receive them within next 7 days.	No PD review	Include
16.	Did not meet I-E criteria but randomized	Participant met exclusion criterion	Participant met exclusion criterion 12: A known sensitivity or allergy to any components of the study vaccine.	No PD review	Include
17.	Did not meet I-E criteria but randomized	Participant met exclusion criterion	Participant met exclusion criterion 13: History of allergy to antibiotic kanamycin.	No PD review	Include

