37.	Temperature excursion	Temperature excursion: transit/ storage (IP)	Vaccine has been administered despite a storage temperature deviation not approved by the sponsor or vaccine has been administered from a batch where the temperature was not monitored.	PD review	Decision will be taken on the case by case basis during the review of final protocol deviation listing performed prior to database lock

N	Protocol Deviation Category	Protocol Deviation Subcategory	Detailed Exclusion Description	PD Assessment	Decision for Per Protocol Population
38.	Inappropriate Blood Collection / Processing	Blood sample not processed correctly as per requirement	Blood sample for immunogenicity not processed correctly as per requirement	PD review	Decision will be taken on the case by case basis during the review of final protocol deviation listing performed prior to database lock
39.	Study vaccine administration	Incorrect route of vaccine administration	Incorrect route of vaccine administration	No PD review	Exclude
40.	Study drug administration	Vaccine has been administered out of the expiration date at the time of administration without sponsor's approval.	Vaccine has been administered out of the expiration date at the time of administration without sponsor's approval.	No PD review	Exclude
41.	Informed Consent Not Taken	--	Informed Consent is Not Taken at screening visit	No PD review	Exclude
42.	Incorrect/Unapproved ICF version used	--	Incorrect/Unapproved ICF version is used at screening visit	No PD review	Include
43.	Incorrect Informed consent process followed	Impartial Witness not used	Impartial Witness is not used at screening visit	No PD review	Include
44.	Dosed when withdrawal / discontinuation criteria met.	Dosed when withdrawal / discontinuation criteria met. (except discontinuation reason - Prohibited Medication)	Participant is discontinued from the study with any reason except discontinuation reason - Prohibited Medication	No PD review	Include
45.	SAE not reported within timelines	Initial SAE reporting not done within the timelines	Initial SAE reporting is not done within the timelines	No PD review	Include

N	Protocol Deviation Category	Protocol Deviation Subcategory	Detailed Exclusion Description	PD Assessment	Decision for Per Protocol Population

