12.1 Immunogenicity

GMC along with the two-sided 95% CI is calculated by exponentiation of the anti-log of the arithmetic mean of the \log_{10} -transformed concentrations. GMC along with the two-sided 95% CI for IgA at baseline and 28 days after the second vaccination will be summarized descriptively by vaccine group for the PP and FA population (Tables 14 and 15, respectively).

Non-inferiority in the immunogenicity of ROTAVIN in comparison to ROTAVIN-M1® is defined as the ratio of GMCs between ROTAVIN and ROTAVIN-M1® is larger than 1/2. The following hypothesis will be tested:

$$H_0: \text{GMC}_{\text{ROTAVIN}}/\text{GMC}_{\text{ROTAVIN-M1}} \leq \frac{1}{2}$$

$$H_1: \text{GMC}_{\text{ROTAVIN}}/\text{GMC}_{\text{ROTAVIN-M1}} > \frac{1}{2}$$

The ratio of GMCs between ROTAVIN and ROTAVIN-M1® along with the two-sided 95% CI is calculated using the log₁₀-transformed anti-rotavirus IgA concentrations to construct a two-sided 95% CI for the mean difference between the two study vaccines using the t-distribution. The mean difference and corresponding 95% CI are exponentiated to obtain the GMC ratio and the corresponding 95% CI. If the lower limit of the 95% CI of the ratio of GMCs between ROTAVIN and ROTAVIN-M1® is larger than 1/2, ROTAVIN is considered to be non-inferior to ROTAVIN-M1®. This results in a one-sided type I error rate of 0.025.

The ratio of the GMCs 28 days after the second dose will be provided along with the two-sided 95% CI for the PP and FA population (Tables 14 and 15, respectively).

The non-inferiority test on the 95% CI for the ratio of GMCs on the PP population is considered the primary analysis. The remaining immunogenicity analyses are considered supportive.

If the serum anti-rotavirus IgA antibody concentration is below the lower limit of quantitation (LLOQ), i.e. assay is recorded as “<LLOQ”, then the concentration will be set to half that limit (LLOQ/2). If the concentration is above the upper limit of quantitation (ULOQ), an actual value will be reported.

An analysis of covariance (ANCOVA) model with the log₁₀-transformed concentrations as the dependent variable, the vaccine group as the explanatory variable, and the log₁₀-transformed baseline concentrations as a covariate will also be performed for the PP and FA population (Tables 14 and 15, respectively). This adjusted analysis will be considered as supportive.

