Yes	x (x)	x (x)	x (x)
No	x (x)	x (x)	x (x)
Pregnancy in any family member living in the same household	x (x)	x (x)	x (x)
Yes	x (x)	x (x)	x (x)
No	x (x)	x (x)	x (x)

N=Total number of participants in the safety population
x=Number of participants with an event
Percentages are based on the total number of participants in the safety population.

Table 6: Protocol Deviations by Category – Safety Population

Protocol Deviation Category	ROTAVIN N=XX x (%), E	ROTAVIN-M1 N=XX x (%), E	Total N=XX x (%), E
Total	x (%), E	x (%), E	x (%), E
Incomplete vaccination: Subject declined further vaccination but safety follow up continued	x (%), E	x (%), E	x (%), E
Incorrect Informed consent process	x (%), E	x (%), E	x (%), E
Incorrect Procedure	x (%), E	x (%), E	x (%), E
Missed Procedures	x (%), E	x (%), E	x (%), E
Subject confidentiality compromised: Personal data of subject transmitted to unintended recipient/s	x (%), E	x (%), E	x (%), E
Temperature excursion	x (%), E	x (%), E	x (%), E
Visit Window Deviation: Post vaccination assessment done before protocol specified timeline	x (%), E	x (%), E	x (%), E
Other	x (%), E	x (%), E	x (%), E

N=Total number of participants in the safety population E=Total number of protocol deviations x=Number of participants with a protocol deviation Percentages are based on the total number of participants in the safety population.
			

If multiple protocol deviations are reported for a participant, the participant may be counted in multiple rows corresponding to the different protocol deviation categories; however, they will be counted only once in the "Total" row. Therefore, the sum of participants may not add up to the "Total" row.

Programming Note: Print only the categories that have data

Table 7: Protocol Violations by Category – Safety Population

Protocol Violations Category	ROTAVIN N=XX x (%), E	ROTAVIN-M1 N=XX x (%), E	Total N=XX x (%), E
Total	x (%), E	x (%), E	x (%), E
Did not meet I / E criteria but enrolled	x (%), E	x (%), E	x (%), E
Dosed when withdrawal / discontinuation criteria were met	x (%), E	x (%), E	x (%), E
Incomplete vaccination: Replacement dose not administered in case of vomiting within 5 mins of administration	x (%), E	x (%), E	x (%), E
Informed Consent Not Taken	x (%), E	x (%), E	x (%), E
Incorrect Informed consent process: LAR not used when required	x (%), E	x (%), E	x (%), E
Damaged / Expired IP / Quarantined kit used without prior approval	x (%), E	x (%), E	x (%), E

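### SAP Table A2 row 44 keeps infants dosed after a discontinuation criterion in the per-protocol set without review, which conflicts with the enrolment rows for some conditions

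*SAP*

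**What the plan says.** Table A2 (SAP section 9, Protocol Compliance) assigns each type of deviation a per-protocol (PP) decision.

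- **Row 44.** The subcategory is "Dosed when withdrawal / discontinuation criteria met. (except discontinuation reason - Prohibited Medication"; the description is "Participant is discontinued from the study with any reason except discontinuation reason - Prohibited Medication". The assessment is No PD review and the decision is Include.
- **PP definition.** SAP 7.1 requires "no major protocol deviations that are determined to potentially interfere with the immunogenicity assessment of the study vaccines". SAP 12.1 states: "The non-inferiority test on the 95% CI for the ratio of GMCs on the PP population is considered the primary analysis".
- **Bar to the second dose.** Protocol 5.1.3 lists absolute contraindications, among them severe combined immunodeficiency and "Detection of one or more of the exclusion criteria during dosing period". It lists fever, acute disease and gastroenteritis within 72 hours separately, as contraindications at that point in time.
- **Enrolment rows.** Rows 5 to 22 cover infants who failed an exclusion criterion but were randomized. Row 12, for example, excludes "Known or suspected impairment of immunological function based on medical history and physical examination".
- **Violation class.** SAP Table 7 lists "Dosed when withdrawal / discontinuation criteria were met" as a protocol violation. Protocol 17 defines a violation as a departure "which may affect the safety of trial participants or the study outcomes".
- **Review.** Protocol 12.3.3 provides for blinded review of PP exclusions. Rows marked No PD review are settled in advance.

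**The concern.** Rows 5 to 22 apply to eligibility at randomization. If one of the same conditions is first found before Dose 2 and the infant is dosed anyway, row 44 is the row that fits, and it says Include with no review. Suspected immune impairment would then remove an infant from the primary population if found at Dose 1, but not if found at Dose 2. The PP definition is meant to keep out deviations that could disturb the immune response, so for such infants the table would work against the definition.

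This matters because the primary test is a non-inferiority test. Infants who respond poorly for reasons unrelated to formulation, if present equally in both arms, pull the GMC ratio towards 1 and make non-inferiority easier to declare.

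The row is also hard to program. Its subcategory is a dosing event and its description is study discontinuation, which are different groups of infants.

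**Working it through.** **1. Row 44 against the enrolment rows**

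| Exclusion criterion | Enrolment row and decision | Row 44 if first found before Dose 2 |
|---|---|---|
| 8 immune impairment | 12, Exclude | conflicts |
| 5 severe malnutrition | 9, Exclude | conflicts |
| 15 persistent diarrhoea | 19, Exclude | conflicts |
| 4, 6, 18 (other trial, systemic disorder, other medical condition) | 8, 10, 22, PD review | removes the review |
| 1 diarrhoea or vomiting within 72 h | 5, Exclude | depends on whether the term covers temporary contraindications |
| 2 fever, 3 acute disease | 6, 7, Include | agrees |
| 7 abdominal disorder or intussusception | 11, Include | agrees |
| 12 allergy to a component, 14 congenital defect | 16, 18, Include | agrees |
| 10 outside rotavirus vaccine, 16 immunoglobulin or blood products | 14, 20, Exclude | no gap: rows 26 and 27 exclude receipt during the study |

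Over all 18 criteria, the enrolment rows exclude 7 (1, 5, 8, 10, 15, 16, 17), include 8 (2, 3, 7, 9, 11, 12, 13, 14) and review 3 (4, 6, 18). The clear conflict is therefore three criteria, plus three that lose their review and one that is uncertain. Criterion 17 (immunosuppressants, row 21) is not counted, since row 26 also excludes prohibited medication.

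**2. The plan's own power figure**

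Inputs from Protocol 12.2: 250 vs 125 evaluable, SD of log10 IgA 0.8, margin 0.5 (log10 2 = 0.301), one-sided alpha 0.025.

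- Standard error = 0.8 × √(1/250 + 1/125) = 0.0876.
- Power = Φ(0.301/0.0876 − 1.96) = 93.0%; the exact noncentral t gives 92.9%. The stated 93% is reproduced.

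**3. Effect of keeping such infants**

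Assumptions, not taken from the plan: a share p in each arm does not respond at all, and the true ratio among the rest is 0.5. Non-responders sit at the vaccine group's pre-vaccination GMC of 5.72 in the earlier phase III trial, against a post-vaccination GMC of 85.9 (Protocol 2.5.3, Table 2.11).

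- Expected ratio = 10^(−0.301 × (1 − p)).
- Variance v = (1 − p) × 0.64 + p(1 − p) × (log10 85.9 − log10 5.72)², where the squared difference is 1.384. The same v is used in both arms.
- Standard error = √(v × (1/250 + 1/125)).
- Type I error = 1 − Φ(1.96 − 0.301p / standard error).

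For p = 1%: v = 0.6336 + 0.0137 = 0.647, standard error 0.0881, shift 0.00301/0.0881 = 0.034, so type I error = 1 − Φ(1.926) = 2.7%.

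| Share p | Expected ratio | One-sided type I error |
|---|---|---|
| 0 | 0.500 | 2.5% |
| 0.5% | 0.502 | 2.6% |
| 1% | 0.503 | 2.7% |
| 2% | 0.507 | 2.9% |
| 5% | 0.518 | 3.7% |

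Of 375 evaluable infants, 1% is about 4 (0.01 × 375 = 3.75) and 5% is about 19 (0.05 × 375 = 18.75).

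**4. Effect of removing them**

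Exact t power at true ratio 1, SD 0.8: 249/124 gives 92.7%, 248/124 gives 92.7%, 245/122 gives 92.3%, 238/119 gives 91.7%. The largest loss is 92.9 − 91.7 = 1.2 points, at a 5% share. Keeping a 5% share of non-responders also leaves about 91.7% (normal approximation), so removal loses little against keeping them.

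**The case against.** **The criteria may not be those of Protocol 5.1.3.** Neither document defines withdrawal or discontinuation criteria by that name. The schedule of events lists a check of withdrawal criteria separately from the check of contraindications. Protocol 7.4 lists withdrawal reasons such as withdrawn consent, non-compliance and loss to follow-up, and row 44's description resembles that list. On that reading Include is unremarkable. The ambiguity is real. However, the subcategory concerns dosing, and the carve-out for prohibited medication fits eligibility-type criteria better. An infant who has left the study would also usually have no Day 85 result and drop out under row 29 or 46, so Include has practical effect mainly on the 5.1.3 reading.

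**A safeguard exists.** Protocol 8.2 withholds the blood sample when the principal investigator or medical monitor judges that a deviation might have influenced the immune response. That removes some of these infants in practice. It is a judgement on sampling and not a PP rule.

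**Stronger readings that the documents do not support.**

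- A reader might infer that row 44 contradicts the enrolment rows generally. It does not, as the comparison above shows: several rows also say Include, and rows 26 and 27 close other gaps.
- A reader might treat gastroenteritis as a plain bar to Dose 2. Protocol 5.1.3 makes it a temporary contraindication, so its place under row 44 is unknown.
- A reader might argue that a protocol violation must leave the PP set. The definition covers safety as well as outcomes. Table 7 also lists late safety reporting as a violation, while row 45 keeps late SAE reports in the PP set.

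**Conclusion.** The point holds in limited form. If row 44 refers to the criteria of Protocol 5.1.3, Table A2 treats immune impairment, severe malnutrition and persistent diarrhoea differently according to whether they are found at enrolment or before Dose 2. It also removes the review given at enrolment to criteria 4, 6 and 18. Diarrhoea or vomiting within 72 hours may belong on the list, subject to the missing definition. Apart from this, the row's description does not match its subcategory on any reading.

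The effect on the primary result is probably small. The documents do not say how often such dosing is expected. The type I error figures assume complete non-response, which is extreme because these infants also received Dose 1, and equal shares in both arms. An unequal split could move the ratio either way. The full analysis population gives a supportive check but does not decide non-inferiority. The change is worth making because the primary population should follow one rule per condition, settled blind before lock.

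**What to change.** Amend row 44 of Table A2 in three ways:

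1. Change the assessment to blinded PD review. The PP decision should follow the enrolment row for the same condition: Exclude for rows 9, 12 and 19, and for row 5 if temporary contraindications are covered; case-by-case for rows 8, 10 and 22; Include where the enrolment row says Include.
2. Rewrite the description so that it describes dosing after a criterion was met, in line with the subcategory.
3. Name the protocol section that defines the criteria (5.1.3, 7.4 or both), and state whether temporary contraindications count.

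This edits one SAP row and changes no clinical rule. The cost is a few more cases in the blinded review before lock and, at the assumed shares of up to 5%, at most about 1.2 points of power.
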